14.1 Applicable SOPs

AEs definition, classification and management will follow the CRO's SOPs, based upon applicable local and international regulations. The full SOPs or an operative summary will be made available in the CRO.

A brief summary of AE definition, classification and management is reported below.

14.2 Definition of Adverse Event (AE)

An Adverse Event is "*any untoward medical occurrence in a patient or clinical trial subject administered a medicinal product and which does not necessarily have a causal relationship with this treatment*".

AEs include:

- worsening (change in nature, severity or frequency) of conditions present at the onset of the trial
- patient/subject deterioration due to the primary illness
- intercurrent illnesses
- drug interactions
- events related or possibly related to concomitant medications
- abnormal laboratory values, as well as significant shifts from baseline within the range of normal, which the investigator considers to be clinically significant.

An AE can therefore be any unfavourable and unintended sign (including an abnormal laboratory finding), symptom, or disease temporally associated with the use of an investigational medicinal product, whether or not considered related to the investigational medicinal product.

14.3 Definition of Adverse Drug Reaction (ADR)

An Adverse Reaction is "*any untoward and unintended response to an investigational medicinal product related to any dose administered*".

All AEs judged by either the reporting investigator or the sponsor as having a reasonable causal relationship to a medicinal product qualify as adverse reactions. The expression reasonable causal relationship means to convey in general that there is evidence or matter to suggest a causal relationship.

➤ Unexpected Adverse Drug Reaction

An unexpected ADR is: "*An adverse reaction, the nature, or severity of which is not consistent with the applicable product information (Reference Safety Information [RSI]).*

- **Reference Safety Information (RSI):** in order to assess whether an adverse reaction is expected, the SmPC will be used.

14.4 Definition of Serious Adverse Events or Serious Adverse Drug Reaction

A Serious Adverse Event (SAE) is: “*any untoward medical occurrence or effect that at any dose:*

- results in death
- is life-threatening (i.e. the subject was at risk of death at the time of the event/reaction; it does not refer to an event/reaction which hypothetically might have caused death if it were more severe)
- requires inpatient hospitalization or prolongation of existing hospitalization
- results in persistent or significant disability/incapacity (where disability is defined as a permanent or substantial disruption of ability to carry out normal life functions, either reported or defined as per clinical judgement)
- is a congenital anomaly/birth defect
- is an important medical event that may not result in death, be life-threatening, or require hospitalization but, according to appropriate medical judgment, it may jeopardize the subject and may require medical or surgical intervention to prevent any of the outcomes listed in the definition above. Examples of such events include allergic bronchospasm requiring intensive treatment in an emergency room or at home, and blood dyscrasias or convulsions that do not result in hospitalization, or development of drug dependency or drug abuse.

Any suspected transmission via a medicinal product of an infectious agent is also considered a serious adverse event.

A **Serious Adverse Drug Reaction (SADR)** is an ADR that meets also the definition of SAE.

A **Suspected Unexpected Serious Adverse Reaction (SUSAR)** is an ADR that is both unexpected (not consistent with the applicable product information, e.g. SmPC) and also meets the definition of a SAE.

A non-serious adverse event is any adverse event that does not meet the criteria listed above for a serious adverse event.

14.5 Definition of Severity of Adverse Events

The term “severe” is used to describe the intensity (severity) of a specific event:

- Mild: causing no limitation of usual activities; the subject may experience slight discomfort.
- Moderate: causing some limitation of usual activities; the subject may experience annoying discomfort.
- Severe: causing inability to carry out usual activities; the subject may experience intolerable discomfort or pain.

14.6 Definition of Adverse Event causality

Causality shall be determined according to the definition of ADR given in 14.3.

All AE judged by either the investigator or the sponsor as having a reasonable suspected causal relationship to an investigational medicinal product qualify as adverse reactions. The causality assessment given by the investigator should not be downgraded by the sponsor.

The following binary decision for causality will be used:

- Reasonable possibility that the IMP caused the event
- No reasonable possibility that the IMP caused the event

Features supportive of an association include:

- temporal plausibility
- pharmacological properties of the drug or of the substance class
- course of the adverse event after dechallenge and, if applicable, after rechallenge
- specific tests indicating involvement of the drug in the occurrence/worsening of the adverse event
- alternative explanations

14.7 Adverse Events recording

Each AE occurring to a subject, either spontaneously revealed by the subject or observed by the investigator, whether believed by the investigator to be related or unrelated to the IMP, must be recorded on the AE information page of the CRF (for SAEs information must be recorded also on the “Serious Adverse Event Form”).

The Investigator will also perform an evaluation with respect to seriousness and causality (relationship of any AE to IMP) of the AEs. and record it on the appropriate section of the CRF and on the “Serious Adverse Event Form” (if appropriate).

14.8 AEs monitoring window

- Start of monitoring: from immediately after the signature of the informed consent
- End of monitoring: up to final study visit/ETV (observation window)

An AE occurring after the final visit/ETV and coming to knowledge of the investigator (e.g. during a follow-up assessment or by spontaneous reporting by study subjects) must be recorded only if it is an ADR, according to the investigator’s judgment.

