2 STUDY SCHEDULE (A MORE DETAILED TABLE IS SHOWN IN APPENDIX 1)

ACTIVITIES	Screening	Period 1				Period 2				Final visit/ETV ¹	
		Single Dose				Multiple Dose					
		Visit	V1	V2	V3	V4	V5	V6	V7		
Day	Day -14/-2	Day -1	Day 1/3	Day 4/5	Day 8/9	Day 10/13	Day 14/17	Day 18	Day 18 ²		
Informed consent	x										
Demography	x										
Lifestyle	x										
Medical and surgical history	x										
Physical examination³	x									x	
Prior and concomitant medications	x	x	x	x	x	x	x	x	x		
Height	x										
Body Weight³	x									x	
Laboratory analysis⁴	x									x	
Virology	x										
Serum pregnancy test (women)	x										
Urine multi-drug kit test	x	x									
Blood pressure and heart rate⁵	x		x (Day 1: pre-dose, 2 hours post-dose)	x (Day 5: 96 hours after Day 1)	x (Day 8: pre-dose, 2 hours post-dose)	x (daily from Day 10 to Day 13: pre-dose)	x (Day 14: pre-dose, 2 hours post-dose)	x (Day 18: 96 hours after Day 14)		x	
Alcohol breath test		x									
Urine pregnancy test (women)		x								x	
ECG⁶	x									x	
Inclusion/exclusion criteria	x	x									
Subject eligibility	x	x									
Enrolment and randomisation		x									
Confinement		x	x	x	x	x	x	x			
Discharge									x		
Investigational product administration			x ⁷ (Day 1)		x ⁷	x ⁷	x ⁷ (Day 14)				
Blood sampling for PK analysis			x ⁸	x ⁸	x ⁹	x ¹⁰	x ⁸	x ⁸			
Standardized meals¹¹		x	x	x	x	x	x	x			
Adverse event monitoring¹²	x	x	x	x	x	x	x	x	x		

1. *Early termination visit (ETV)*
2. *Final visit on day 18*
3. *Physical examination, including body weight, at screening and final visit/ETV*
4. *Laboratory analyses at screening and final visit/ETV*
5. *At pre-dose (before blood sampling and within 30 min of investigational product administration), at 2 h (± 15 min) and 96 h (± 15 min) after day 1 single dose and after day 14 last multiple dose. At pre-dose (before blood sampling and within 30 min of investigational product administration), and 2 h (± 15 min) after the day 8 first multiple dose. At pre-dose (before blood sampling and within 30 min of investigational product administration) on day 10 to day 13.*
6. *At screening and final visit/ETV*
7. *On day 1 (Period 1) and once daily from day 8 to day 14 (Period 2), at 8:00 \pm 1 h*
8. *At pre-dose (0), 0.5, 1, 1.5, 2, 3, 4, 6, 8, 12, 16, 24, 36, 48, 72 and 96 h post-dose after the first single dose (day 1) and the last multiple dose (day 14);*
9. *At pre-dose (0) and 0.5, 1, 1.5, 2, 3, 4, 6, 8, 12, 16 and 24 h post-dose after the first multiple dose (day 8)*

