7.2 Discussion of design

Following a specific request of CFDA, the present study will be part of safinamide registration package in China and was designed according to CFDA guideline recommendations (1).

Safinamide has recently been granted marketing authorization in EU, Norway and Switzerland on the basis of the results of clinical trials performed in European countries. In the present study, safinamide pharmacokinetic profile, safety and tolerability after single dose and at steady state will be investigated for the first time in Chinese healthy male and female volunteers.

Two single doses (i.e. 50 and 100 mg) of safinamide will be administered to two subject¹ cohorts. The study will continue with multiple administrations of safinamide 50 and 100 mg, orally taken once a day for 7 days.

The 50 and 100 mg oral doses have been selected according to the common clinical practice (see Xadago[®] SmPC). These doses were investigated in the previously performed Phase III clinical trials. The volunteers will be assigned to the two cohorts according to the study randomised, parallel-group design.

Safinamide pharmacokinetic profile will be investigated after single dose, according to CFDA guidance requirements, and at steady state since multiple doses are administered in the clinical practice. Safinamide steady state should be reached after 5 or 6 days of treatment (day 13-14 in this study). Safinamide pre-dose concentrations will be assessed before the last 5 doses (days 10-14).

An open design was chosen. However, no bias on study outcome is expected considering that the study PK endpoints are based on the objective measurement of safinamide in plasma. Blood sampling time-points were selected on the basis of the known PK profile of safinamide. The sampling time lasts for about 4-7 elimination half-lives (mean PK half-life: 20-23 h) after both single dose and the last multiple dose administration.

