9.1 Study visits and procedures

Each study subject completing the study will undergo 8 visits plus a final visit.

The study protocol foresees 2 periods: in the first one the investigational products are administered in single dose, in the second one in multiple doses. The single dose in the first period and the first dose in the second period are separated by a wash-out interval of 7 days. Maximum and minimum study duration will be 32 and 20 days, respectively, screening visit included.

The first subject first visit (FSFV) is defined as the 1st visit performed at the clinical centre by the 1st screened subject. The last subject last visit (LSLV) is defined as the last visit performed at the clinical centre (or a telephonic follow-up, if applicable) by the last subject, i.e. the last visit foreseen by the study protocol, independently of the fact that the subject is a completer or a withdrawn subject.

The following phases, visits and procedures will be performed:

➤ Screening phase

- Screening – visit 1: between day -14 and day -2
- Period 1 – visit 2: day -1

➤ Interventional phase

- Period 1 – visit 3: days 1-3: single dose and blood sampling for PK analysis
- Period 1 – visit 4: days 4-5: blood sampling for PK analysis
- Wash-out interval of 7 days
- Period 2 – visit 5: days 8-9: first multiple dose and blood sampling for PK analysis
- Period 2 – visit 6: days 10-13: multiple doses and blood sampling for PK analysis
- Period 2 - visit 7: days 14-17: last multiple dose and blood sampling for PK analysis
- Period 2 - visit 8: day 18: blood sampling for PK analysis

➤ Final phase

- Final visit/early termination visit (ETV). In case of early discontinuation, discontinued subjects will undergo an early termination visit (ETV)

Study schedule

	Day	Procedures/Assessments	Notes
Screening – Visit 1	From day -14 to day -2	
 ➤ Explanation to the subject of study aims, procedures and possible risks ➤ Informed consent signature ➤ Subjects' screening number assignment ➤ Demographic data and lifestyle recording ➤ Medical/surgical history ➤ Previous/concomitant medications check ➤ Full physical examination (body weight, height, vital signs, physical abnormalities) ➤ ECG recording ➤ Clinical laboratory analyses: haematology, blood chemistry, urinalysis, serum virology and serum pregnancy test (women) ➤ Urine multi-drug kit test ➤ Adverse events check ➤ Inclusion/exclusion criteria evaluation ➤ Eligibility evaluation 	

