Period 2 Cohorts 1 and 2 - Visit 8	Day 18	
Day 18
 
 ➤ Blood sample collection for pharmacokinetic analysis at 96 h post-dose ➤ Vital signs measurement at 96 h post-dose (± 15 min) from Day 14 ➤ AEs and concomitant medications check 
➤ Final visit assessments (see below) and discharge
	
Day 18
 
Standardized breakfast (after PK sampling).
 
Subjects will be discharged after final visit assessments (see Final visit/ETV below)

Final Visit/ETV	Day 18. At ETV in case of early termination	
The following final assessments will be performed after the 96-h time-point assessments (day 18) or at ETV in case of early discontinuation:
 
 ➤ Physical examination (body weight, physical abnormalities) ➤ ECG recording ➤ Laboratory analyses: haematology, blood chemistry, urinalysis ➤ Urine pregnancy test (women) 
Vital signs assessments performed at 96 h post-dose (± 15 min) on day 18 will be considered as the final assessment. Vital signs will also be measured at ETV, in case of early discontinuation.
 
AEs and concomitant medications will also be checked at final visit/ETV. AEs will be captured up to the end of study visit.
 
In case of clinically significant results at the final visit, the subjects will be followed-up by the investigator until the normalisation of the concerned clinical parameter(s)
	
Upon leaving, the subjects will be instructed to contact immediately the investigator in case of occurrence of any adverse reactions

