17.4.2 Discontinuation procedures

For any subject discontinuing the study, the investigator will:

- ask the subject to undergo, as far as possible, a final medical visit (ETV) to examine the subject's health conditions and perform the required blood sampling for the laboratory

assays. This examination will verify that all values tested at screening have remained within a clinically acceptable range (i.e. not clinically significant changes compared to screening)

- arrange for alternative medical care of the withdrawn subject, if necessary
- record the subject decision about the use of collected biological samples
- report in the CRF date and time of the last dose administration, and date and primary reason of study discontinuation
- record in the CRF any follow-up, if the subject is withdrawn for an AE

Discontinued subjects will not be replaced.

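### Active adverse-event collection ends at the early termination visit, which has no minimum time after the last dose, while completers are followed for 96 h

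*Protocol*

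**What the plan says.** Protocol v3.0, section 14.8, starts AE monitoring at consent and closes it with "End of monitoring: up to final study visit/ETV (observation window". An event that comes to light afterwards "must be recorded only if it is an ADR", on the investigator's judgement.

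For completers the closing visit has a fixed position. Dosing is "On day 1 (Period 1) and once daily from day 8 to day 14 (Period 2"), and section 9.1 places the final assessments as follows: "The following final assessments will be performed after the 96-h time-point assessments (day 18) or at ETV in case of early discontinuation". For early leavers the same sentence gives a visit but no time. Section 9.1 also says "In case of early discontinuation, discontinued subjects will undergo an early termination visit (ETV"), and section 17.4.2 tells the investigator to "ask the subject to undergo, as far as possible, a final medical visit (ETV"). Neither gives a day, an hour or an interval from the last dose. Nor do the schedule table in section 2, section 10.1.2 or Appendix 1.

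Four provisions operate after the ETV:
- Section 14.8: adverse drug reactions (ADRs) that reach the investigator are recorded.
- Section 14.10: an AE requiring discontinuation is followed until it subsides or stabilises.
- Section 14.9.1: late serious events go to the authorities and ethics committee, and related ones also to the sponsor, though not into the CRF.
- Section 9.1: departing subjects are told to contact the investigator about adverse reactions, and clinically significant final-visit results are followed up.

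The treatment-emergent AE (TEAE) definition (Protocol 13.5.1, SAP v2.0 section 3.2.3.1) starts at the first dose and has no end point. SAP 4.5.2 keeps anyone with at least one dose in the safety set, and SAP 4.2 uses the full set as the percentage denominator.

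**The concern.** Safety and tolerability form the secondary end-point. A TEAE percentage assumes that the subjects in its denominator had a comparable chance of having an event recorded. Here completers get four days of active observation after their last dose, and early leavers get whatever interval happens to precede the ETV. The same mild headache 24 h after a last dose, judged unrelated, would be recorded for a completer but not for a subject whose ETV was held earlier that day. A shortened window can only miss events, and its owner still contributes a full unit to the denominator. With cohorts of 12, one missed subject matters to a descriptive table.

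**Working it through.** **Inputs.** Last dose for completers: day 14; final visit: day 18 (Protocol sections 2 and 9.1). Half-life: "mean PK half-life: 20-23 h" (section 7.2). Time to peak: 1.8-2.8 h (section 4.1.2). Planned size: 12 per cohort, at least 8 completers (section 13.2).

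**1. The completers' interval.** (18 − 14) days × 24 h = 96 h, which reproduces the protocol's 96 h time point. In half-lives: 96/23 = 4.2 to 96/20 = 4.8.

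**2. Drug remaining when the window closes.** Fraction left = 0.5^(t / half-life):

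| Time from last dose to closing visit | Half-life 20 h | Half-life 23 h |
|---|---|---|
| 2 h | 93.3% | 94.2% |
| 3 h | 90.1% | 91.4% |
| 24 h | 43.5% | 48.5% |
| 96 h (completers) | 3.6% | 5.5% |

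**3. Check allowing for absorption.** Assume a one-compartment oral model, with the absorption rate ka solved from tmax = ln(ka/k)/(ka − k), where k = ln 2/half-life. Over both half-lives and both times to peak, after a single dose and after the seventh daily dose, concentration is 93-100% of peak at 2-4 h, 47-54% at 24 h and 4-6% at 96 h. After a single dose, the share of that dose's AUC falling inside the window is 4-12% for an ETV at 2-4 h, 50-56% at 24 h and 94-96% at 96 h.

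**4. Who can be affected.** Only a subject whose ETV falls less than 96 h after the last dose. Someone who takes the day 1 dose and leaves after the day 5 assessments but before day 8 already has the full interval. An ETV within hours of a dose requires leaving on day 1 or on days 8-14.

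**5. Size.** The plan allows 12 − 8 = 4 early leavers of 12 (33%) per cohort. If all 12 are dosed, each subject whose event is missed lowers that cohort's incidence by 1/12 = 8.3 percentage points. SAP 4.11.1 lists as most common any preferred term reported by more than 5% of subjects in a cohort, so one subject decides whether a term appears. The number of events missed cannot be derived from the documents.

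**The case against.** The strongest reply is that the protocol does not abandon these subjects. A subject who leaves because of an AE has that event counted and followed under section 14.10. Late ADRs and serious events still have a route, the ETV includes an examination, ECG and laboratory tests, and the analysis is descriptive. All of that stands. It narrows the gap to active collection of new events, and to non-serious events judged unrelated, but does not close it.

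A reader might also infer more than the documents support:

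- **That late events are lost by rule.** Causality is binary (section 14.6) and temporal plausibility counts in favour of a link, so a doubtful event soon after a dose can be classed as an ADR and recorded. Late serious events are reported to the authorities whatever their cause.
- **That early leavers are cut off at the highest exposure.** A same-day ETV is permitted, not scheduled. Steady-state accumulation under daily dosing is 1/(1 − 0.5^(24/half-life)), or 1.8 to 1.9, so a subject leaving after the single day 1 dose has roughly half a completer's steady-state exposure.
- **That counts are biased most where tolerability is worst.** AE is one of eleven discontinuation reasons in section 17.4.1, and nothing shows that early leavers generally tolerate the drug less well.
- **That section 14.8 conflicts with 14.3 and 14.6 over who judges causality.** Section 14.8 governs what the investigator records after the window; the other two govern who may classify an AE as an ADR.

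**Conclusion.** The asymmetry is real in the current text. Active, all-cause AE collection runs to 96 h after the last dose for completers, with about 4-6% of the drug remaining, and to an untimed visit for early leavers, with 44-49% remaining at 24 h and over 90% within about 3 h of a dose. These figures rest on the protocol's half-life and simple exponential decline; the absorption model agrees.

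Because early leavers stay in the denominators, any effect on TEAE counts is downward. Its size is unknown: it depends on how many subjects leave, when their ETVs are held and what would have been reported. Four of 12 per cohort is the design's allowance, not a forecast. This is a cheap improvement to data collection, not a flaw that undermines the safety analysis.

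**What to change.** In section 14.8, define the end of the AE window as the final visit or, for discontinued subjects, the later of the ETV and 96 h after the last dose. State that all AEs are recorded to that point regardless of causality, and repeat this in section 17.4.2. If the ETV takes place before 96 h, require one telephone AE check at or after 96 h. The call must be newly specified: section 9.1 mentions telephone follow-up only in defining the last subject's last visit and attaches no AE check to it.

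The 96 h is the protocol's own interval for completers, so the change equalises observation without touching any dose or treatment rule. The TEAE definition is open-ended, so events from the longer window enter the planned tables without a new analysis rule.

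Cost: two sentences in the next amendment and at most one call per early leaver. A withdrawn subject may decline or be unreachable, in which case that is documented.

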14.9 Adverse Events reporting

The official language for reporting is English. The investigator and clinical staff of the present study are familiar with English language.

The investigator must report to the CRO all AEs which occur during the study, regardless of their relationship to the IMP. Protocol specific AEs or laboratory abnormalities critical to safety

evaluations are to be identified in the protocol and reported to the sponsor according to reporting requirements and within the time periods specified.

All AEs are recorded by the investigator on the AE information page of the CRF.

In addition, SAE will have to be reported according to the following detailed procedure.

14.9.1 *SAEs reporting*

The investigator must report the SAEs to the CRO no later than 24 hours from when he/she becomes aware of the SAE, by Electronic Data Capture (preferred method), or e-mailing as scanned attachment (back up plan) or by faxing the "Serious Adverse Event Form" (back up plan) to the CRO, as stated in the "List of CRO/ personnel" in § 14.13 of this protocol.

The standards of confidentiality must always be maintained and any relevant national legislation on data protection must be followed.

Another copy of the "Serious Adverse Event Form" will be sent to the Medical Affairs/Clinical Operations for the Sponsor's file and another copy will be retained by the Investigator for the Investigator's file.

If the investigator becomes aware of any SAE occurred to a subject within the follow-up window established in the protocol, he/she will report the SAE as above. The SAE will be also reported in the CRF.

If outside the follow-up window established in the protocol the investigator becomes aware of a SAE, if the investigator judges that the SAE is related to the study drug, it should be reported to the Sponsor. The Investigator might use the "Serious Adverse Event Form" via email or fax, but the SAE must not to be reported in the CRF, as it is not an event occurred within the study period.

The investigator must report all SAEs that occur to the subjects to National Medical Products Administration/Local Ethics Committee/Provincial Food and Drug Administration/National Health and Family Planning Commission immediately no later than 24 hours from when he/she becomes aware of SAE. Any SAEs that happen to the subjects outside the follow-up window should be reported by investigator to National Medical Products Administration/Local Ethics Committee/Provincial Food and Drug Administration/National Health and Family Planning Commission immediately.

14.10 *Follow-up for Adverse Events*

A follow-up "Serious Adverse Event Form" will be filled in if important follow-up information (i.e. diagnosis, outcome, causality assessment, results of specific investigations) is made available after submission of the initial AE Form for immediate reporting. Follow-up "Serious Adverse Event Form" will be reported to the Sponsor as above-described, under Section 14.9.1.

In any case of an AE that, in the opinion of the investigator, requires the subject's discontinuation, follow-up information relating to the subject's subsequent course must be collected until the event has subsided or the condition stabilised or when the subject is lost to follow up or death.

When follow-up data on non-serious AE are collected, information should be reported under "Comments" in the Final report of the CRF.

